10.5.5. Anti-tumor Activity

ORR is defined as the proportion of subjects achieving a best response of CR or PR according to RECIST v1.1. CBR is defined as the proportion of subjects achieving a best response of CR/PR or stable disease over a period of ≥ 2 consecutive response assessment time points. Subjects with mCRPC will be assessed for response/clinical benefit per PCWG3 guidelines. DOR is defined as the date from first occurrence of CR or PR to the date of documented PD or death. In assessing DOR, a subject alive and without disease progression will be censored at the date of the last evaluable disease assessment. PFS is defined as the date of initiation of study treatment to the date of documented PD or death from any cause, whichever occurs first. OS is defined as the date of initiation of study treatment to the date of death from any cause.

The 2-sided exact CI using the Clopper-Pearson method will be calculated for response/clinical benefit rates where applicable ([Clopper and Pearson, 1934](#)). Distributions for PFS, DOR, and OS will be estimated by Kaplan-Meier methodology.

The CBR will be summarized by response assessment timepoints (ie, every 2 cycles).

Summary tables of best ORR, PFS, and OS will be provided overall and by malignancy if necessary. Efficacy listings will be provided that include best response, first CR/PR date, last date with CR or PR, most recent date without progression, progression date, death date, and last tumor assessment date, etc. The definition of each response category is provided in RECIST v1.1.

[Table 12](#) provides an overview of the planned efficacy analysis.

Table 12: Anti-tumor Assessments

Endpoint	Analysis Sets	Statistical Method
Objective response rate (ORR)	Dose Expansion and Optimization cohorts	Exact CI
Progression-free survival (PFS)	Dose Expansion and Optimization cohorts	Kaplan-Meier
Duration of response (DOR)	Dose Expansion and Optimization cohorts	Kaplan-Meier
Overall survival (OS)	Dose Expansion and Optimization cohorts	Kaplan-Meier
Clinical benefit rate (CBR)	Dose Expansion and Optimization cohorts	Exact CI

CI=confidence interval.

Note: Anti-tumor analyses may include patients in dose escalation phase.

10.5.6. Pharmacokinetics

PK parameters will be calculated from measurements of KZR-261 plasma concentrations at prespecified timepoints pre- and post-infusion using noncompartmental methods. Other approaches, such as population PK analyses may be considered, if appropriate. PK parameters to be calculated (if adequate data are available for estimation) will include, but not be limited to, C_{max} , AUC, $t_{1/2}$, CL, and V_z . Concentrations and PK parameters of KZR-261 will be summarized for each dose level by cycle and day in Part 1 using descriptive statistics.

10.5.7. Exploratory Assessments

Assessments of various pharmacodynamic study readouts as a function of dose and time post-administration will be described and related to anticancer activity, PK, and safety parameters ([Section 7.4.1](#)).

10.5.8. Handling of Missing Data

Subjects discontinue study treatment and/or the study for any reason will be included in all analyses regardless of the duration of treatment. There will be no imputation for missing data, unless otherwise specified in the Statistical Analysis Plan.

10.6. Interim Analyses

The Go/No-Go futility analysis for each tumor-specific cohort in Part 2A will be based on CBR as the primary outcome measurement (as defined in [Section 10.5.5](#)) after Stage 1 enrollment of 15 subjects. Each of the expansion cohorts is based on the following assumptions:

- Each expansion cohort has a maximum sample size of 35 with one interim futility analysis at 15 subjects. At the interim analysis, if there is 1 or no subject with CBR (ie, CBR rate <7%), further enrollment into the cohort will be stopped for futility. If futility is rejected at the interim analysis (ie, 2 or more of 15 subjects with clinical benefit), the final analysis will be based on a total 35 subjects (ie, 20 additional subjects evaluable for CBR). Note: Outcomes (ie, presence or absence of clinical benefit) for subjects enrolled in Part 1 with the same tumor type and who received the same dose of KZR-261 as evaluated in the corresponding Part 2A, tumor-specific cohort may be included among the initial 15 subjects at the interim analysis, as described above.

The operating characteristics of this design are presented in [Table 13](#). If the true CBR is less than 5%, there is a reasonable chance to reach the futility criterion at interim. On the other hand, if the true CBR is 20% or higher, the probability to stop for futility is moderately low (<20%).

Table 13: Operating Characteristics of Dose Expansion Phase (Part 2A)

True CBR	Interim Analysis (N=15)		Final Analysis (N=35)		
	Pr(Futility*)	Pr(obs. CBR ≥15% 6 or more subjects with CBR)	Pr(obs. CBR ≥20% 7 or more subjects with CBR)	Pr(obs. CBR ≥25% 9 or more subjects with CBR)	Pr(obs. CBR ≥25% 9 or more subjects with CBR)
5%	83%	<1%	<1%	<1%	<1%
10%	55%	11%	5%	<1%	<1%
15%	32%	39%	25%	7%	7%
20%	17%	67%	54%	25%	25%
25%	8%	86%	78%	52%	52%
30%	4%	95%	92%	76%	76%
35%	1%	98%	97%	91%	91%

CBR=clinical benefit rate; obs.=observed; Pr=probability

* 1 or fewer subjects with CBR among the first 15 subjects.

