3.3. Part 2A: Dose Expansion

Following determination of the MTD/MAD, separate tumor-specific cohorts of subjects will be treated with KZR-261. For all subjects enrolled in a tumor-specific cohort, tumor biopsies (fresh [preferred] or archived) will be requested pre-treatment. For any subject who provides a tumor sample pre-treatment, an additional biopsy of accessible tumor tissue will be requested at either the end of Cycle 2 or at PD, whichever comes first. Pre-treatment tumor biopsies (fresh) will be required for subjects enrolled in the All-Tumors expansion cohort (exceptions to this requirement may be considered after discussion with the Medical Monitor); an additional biopsy of accessible tumor tissue will be required at either the end of Cycle 2 or at PD, whichever comes first.

Fifteen subjects will be enrolled in each tumor-specific cohort (Stage 1), which may be increased up to 35 subjects in total as determined by prespecified futility criteria in Stage 1 ([Section 10.6](#)) and if the tumor type is not selected for investigation in Part 2B. Up to 35 biopsy-evaluable subjects may be enrolled in the All-Tumors cohort.

The following distinct dose expansion cohorts may be evaluated, as depicted in [Figure 1](#).

Tumor-Specific Cohorts

- **Malignant melanoma**—histologically or cytologically confirmed, locally advanced unresectable or metastatic cutaneous or uveal melanomas ([Section 4.2](#)).
- **Malignant mesothelioma**—histologically or cytologically confirmed that is either metastatic or locally advanced and not amenable to surgical resection or local therapies ([Section 4.2](#)).
- **mCRPC**—histologically or cytologically confirmed, locally advanced unresectable or metastatic adenocarcinoma of the prostate that is castration (physical or chemical) resistant([Section 4.2](#)).
- **mCRC**—histologically or cytologically confirmed, metastatic or locally advanced unresectable colorectal carcinoma ([Section 4.2](#)).

All-Tumors Cohort

- **All-Tumors**—any relapsed or refractory solid tumors that are amenable to tumor biopsies ([Section 4.2](#)).

Additional (or different) tumor types may be investigated at the Sponsor's discretion in Part 2 if evidence of anti-tumor activity of KZR-261 during Part 1 or in the All-Tumors cohort in Part 2 supports further evaluation.

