- At the interim analysis, if there is 1 or no subject with clinical benefit (ie, CBR rate <7%), further enrollment into the cohort will be stopped for futility. If futility is rejected at the interim analysis (ie, 2 or more of 15 subjects with clinical benefit), the final analysis will be based on a total 35. Note: Outcomes (ie, presence or absence of clinical benefit) for subjects enrolled in Part 1 with the same tumor type and who received the same dose of KZR-261 as evaluated in the corresponding Part 2A, tumor-specific cohort may be included among the initial 15 subjects at the interim analysis, as described above.

The operating characteristics of this design are presented in [Table 3](#). If the true CBR is less than 5%, there is an 83% probability to reach the futility criterion at interim. On the other hand, if the true CBR is 20% or higher, the probability to stop for futility is 17%.

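### The Stage 1 futility count may include Part 1 outcomes under no outcome-independent rule, so the Table 13 stopping probabilities are not assured

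*Protocol*

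**What the plan says.** Protocol 10.6 sets the design: "Each expansion cohort has a maximum sample size of 35 with one interim futility analysis at 15 subjects". The rule is that "if there is 1 or no subject with CBR (ie, CBR rate <7%), further enrollment into the cohort will be stopped for futility". With two or more, the cohort goes on to 35. The footnote to Table 13 gives the same basis for the futility column: "1 or fewer subjects with CBR among the first 15 subjects".

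A note in the same section says that outcomes of Part 1 subjects with the same tumor type, treated at the Part 2A dose, "may be included among the initial 15 subjects at the interim analysis". The synopsis (Sample Size Estimates) repeats this. So does SAP 5: "may be included among the initial 15 subjects at the interim analysis, as described above". In neither Protocol 10.6 nor SAP 5 does the text above the note contain a selection rule. No section says whether inclusion is all-or-none, how many may count, in what order, who decides, or when. SAP 18 (interim analyses) adds nothing on this, and SAP 19 declares no changes from the protocol.

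Three other places bear on it:
- Protocol 3.1 starts Part 2A after Part 1 has fixed the MTD/MAD, and SAP 4.3 describes the study as open-label and unblinded.
- Protocol 3.3 allows additional or different tumor types in Part 2 "if evidence of anti-tumor activity of KZR-261 during Part 1 or in the All-Tumors cohort in Part 2 supports further evaluation".
- SAP 5 states the operating characteristics as firm numbers, for example "If the true CBR is less than 5%, there is an 83% probability to reach the futility criterion at interim".

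**The concern.** The people who decide whether a Part 1 outcome counts will usually be able to see it. If a benefit is more likely to be counted than a non-benefit, the count no longer follows the binomial distribution behind Table 13, and a weak cohort passes more often. Protocol 10.6 builds the final 35 from the 15 plus 20 more, so selected Part 1 outcomes also carry into the final CBR and its exact interval.

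A second route applies to tumor types added because of Part 1 activity. The responders who prompted the cohort could then be counted towards passing its futility test.

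At stake are up to 20 further subjects per cohort exposed to a first-in-human drug, and the meaning of the stopping probabilities that the plan quotes.

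**Working it through.** **Inputs.** Stage 1 n = 15, stop at 0 or 1 benefits, maximum 35 (Protocol 10.6). Write p for the true CBR and m for the number of eligible Part 1 subjects of one tumor type at the Part 2A dose. The documents do not give m. Protocol 10.1.1 plans 6 to about 12 subjects at the MTD/MAD across all tumor types, so I assume m = 1 to 5. Part 1 and Part 2A are given the same p.

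**1. Reproduce Table 13.** Pr(futility) = (1−p)^15 + 15p(1−p)^14. At p = 10%: 0.206 + 0.343 = 0.549. At 5% and 20% it is 0.829 and 0.167. The plan states 83%, 55% and 17%. Pr(at least 6 of 35, having passed Stage 1) at p = 10% is 0.115, against 11% in the table. Table 13 is therefore a plain binomial calculation on 15 subjects.

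**2. Count all m, whatever their results.** Sum over x ~ Bin(m, p) of P(Bin(15−m, p) ≤ 1−x). This equals P(Bin(15, p) ≤ 1), which is Table 13 exactly. Knowing the outcomes does no harm in itself; letting inclusion depend on them does.

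**3. Count only the Part 1 subjects with benefit.** With x benefits counted and 15−x new subjects, the stopping probability is P(Bin(15, p) ≤ 1) for x = 0, (1−p)^14 for x = 1, and 0 for x ≥ 2. Average over x ~ Bin(m, p). For m = 5, p = 10%: 0.590 × 0.549 + 0.328 × 0.229 + 0 = 0.399.

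| m (assumed) | Pr(futility), p = 5% | p = 10% | p = 20% | Pr(≥6/35), p = 10% |
|---|---|---|---|---|
| Table 13 | 83% | 55% | 17% | 11% |
| 1 | 81% | 52% | 14% | 13% |
| 2 | 79% | 49% | 12% | 14% |
| 3 | 78% | 46% | 10% | 15% |
| 4 | 76% | 43% | 9% | 17% |
| 5 | 74% | 40% | 7% | 18% |

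A milder policy pools all m, but only if at least one had benefit. With m = 4 it gives 77%, 45% and 10% at p = 5%, 10% and 20%.

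**4. Tumor type opened because at least one of m Part 1 subjects benefited, all m then pooled.** Stopping requires exactly one Part 1 benefit and none among the 15−m new subjects. So Pr(futility) = m·p(1−p)^14 / [1 − (1−p)^m]. At p = 5% this is 49% for m = 1 and 54% for m = 5. At p = 10% it is 23% and 28%.

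**The case against.** The strongest reply is that the note describes the carried-over outcome in both directions, benefit or no benefit, so counting only benefits is an unfriendly reading. That is fair: the text permits selection but does not announce it. It does not exclude selection either.

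A reader might go further and infer that Table 13 is wrong, or that one known benefit cuts the futility probability from 83% to 49% at CBR 5%, and that two make stopping impossible. The documents do not support using those figures as the size of the problem. They condition on Part 1 results already seen, and they would be the same under a mandatory count-all rule with one eligible subject who benefited, or two who both did. Only the averaged figures in step 3 measure what optional counting does.

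A reader might also infer that the four named cohorts were chosen on Part 1 responses. Protocol 1.2.1 and 1.2.2 say that they came from nonclinical data, bioinformatics and unmet need. The double-use route in step 4 is documented only for additional or different tumor types.

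Two further points stand. Protocol 10.6 itself claims only a reasonable chance of stopping below 5% and less than 20% at 20% or higher; the selective figures of 74–81% and 7–14% are compatible with that. The exact 83% and 17% in SAP 5 are what lose their footing. And CBR is a secondary endpoint, while the primary aim of Part 2 is safety and the RP2D. Favorable selection makes it less likely, not more likely, that an active cohort is stopped.

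**Conclusion.** The point holds as a gap in the rule, not as an error in Table 13. The stated probabilities are exact if inclusion ignores outcome and the two parts share one true CBR; the plan secures neither. Part 1 subjects need not meet the tumor-specific criteria of Protocol 4.2.2, so the common CBR is itself an assumption. That Part 1 outcomes will be known is inferred from the order of the parts and the open-label design.

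For 1 to 5 eligible subjects, benefit-only counting lowers the futility probability by about 2 to 9 percentage points at CBR 5% and 3 to 15 at CBR 10%. It raises the chance of at least 6 of 35 at CBR 10% by about 1 to 7 points. The effect is larger for a cohort opened on Part 1 activity. This should be corrected before Part 2A opens, but it does not threaten the study's primary objectives.

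**What to change.** In Protocol 10.6, the synopsis and SAP 5, replace the permissive wording with one rule fixed before Part 2A opens:

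- Count all Part 1 subjects of that tumor type treated at the Part 2A dose, in order of first dose, or count none.
- Count none for any cohort opened because of Part 1 activity.
- Report the Stage 1 and final CBR with and without Part 1 subjects.

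The first two items restore the Table 13 figures, given a common CBR; the third lets a reader see whether that assumption matters. The cost is wording in two documents, some lost flexibility, and possibly a few more new subjects in Stage 1. The rule cannot be credibly added once the interim count has been made.

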11. ETHICAL AND ADMINISTRATIVE CONSIDERATIONS

11.1. Compliance Statement

The Investigator(s) and all parties involved in this study should conduct the study in adherence to the ethical principles based on the Declaration of Helsinki, International Council for Harmonisation (ICH) guidelines for current GCP, and the applicable national and local laws and regulatory requirements.

Relevant study documentation will be submitted to the regulatory authorities of the participating countries, according to local/national requirements, for review and approval before the beginning of the study. On completion of the study, the regulatory authorities will be notified that the study has ended.

11.2. Institutional Review Board or Independent Ethics Committee

Before initiation of the study at each study center, the protocol, the ICF, other written material given to the subjects, and any other relevant study documentation will be submitted to the appropriate IEC/IRB. Written approval of the study and all relevant study information must be obtained before the study center can be initiated or the study drug is released to the Investigator. Any necessary extensions or renewals of IEC/IRB approval must be obtained for changes to the study (ie, amendments to the protocol, the ICF, or other study documentation). The written approval of the IEC/IRB together with the approved ICF must be filed in the study files.

The Investigator will promptly report to the IEC/IRB any new information that may adversely affect the safety of the subjects or the conduct of the study. The Investigator will submit written summaries of the study status to the IEC/IRB as required. On completion of the study, the IEC/IRB will be notified that the study has ended.

11.3. Informed Consent and Human Subject Protection

The process of obtaining informed consent must be in accordance with applicable regulatory requirement(s) and must adhere to current GCPs.

Subjects will provide written informed consent before any study-related procedures are performed unless the procedure or assessment is consistent with the standard of care for the underlying malignancy.

The Investigator is responsible for ensuring that no subject undergoes any study-related examination or activity before that subject has given written informed consent to participate in the study unless the procedure or assessment is consistent with the standard of care for the underlying malignancy.

The Investigator or designated personnel will inform the subject of the objectives, methods, anticipated benefits, potential risks, and inconveniences of the study. The subject should be given every opportunity to ask for clarification of any points s/he does not understand and, if necessary, ask for more information. At the end of the interview, the subject will be given ample time to consider the study. Subjects will be required to sign and date the ICF. After signatures are obtained, the ICF will be kept and archived by the Investigator in the Investigator's study file. A signed and dated copy of the subject ICF will be provided to the subject.

It should be emphasized that the subject may refuse to enter the study or to withdraw from the study at any time, without consequences for their further care or penalty or loss of benefits to which the subject is otherwise entitled. Subjects who refuse to give or who withdraw written informed consent should not be included or continue in the study.

If new information becomes available that may be relevant to the subject's willingness to continue participation in the study, a new ICF will be approved by the IEC(s)/IRB(s) (and regulatory authorities, if required). The study subjects will be informed about this new information and reconsent will be obtained.

11.4. Direct Access to Source Data, Source Documents, and Study Records

The Sponsor or its representatives may periodically check a sample of the subject data recorded against source documents at the study site. The study may be audited by the Sponsor and/or regulatory agencies at any time. Investigators will be given notice before an audit occurs.

The Investigator will keep records of all original source data. This might include laboratory tests, medical records, and clinical notes. If requested, the Investigator will provide the Sponsor, applicable regulatory agencies, and applicable review boards with direct access to the original source documents.

11.5. Data Collection and Handling

An EDC system will be used in this study. The study site must define and retain all source records and must maintain a record of any data where source data are directly entered into the data capture system.

Data systems used for the study will have controls and requirements in accordance with local data protection law.

The purpose and use of subject personal information collected will be provided in a written document to the subject by the Sponsor.

11.6. Confidentiality

Monitors, auditors, and other authorized agents of the Sponsor and/or its designate, the IEC(s)/IRB(s) approving this research, and the FDA, as well as that of any other applicable agency(ies), will be granted direct access to the study subjects' original medical records for verification of clinical study procedures and/or data, without violating the confidentiality of the subjects to the extent permitted by the law and regulations. In any presentations of the results of this study or in publications, the subjects' identity will remain confidential.

All personal data collected and processed for the purposes of this study should be managed by the Investigator and his/her staff with adequate precautions to ensure confidentiality of those data, and in accordance with the Health Insurance Portability and Accountability Act, applicable to national and/or local laws and regulations on personal data protection.

11.7. Financing and Insurance

Financing and insurance of this study will be outlined in a separate agreement between the CRO and the Sponsor.

11.8. Audit and Inspection

Study centers and study documentation may be subject to Quality Assurance audit during the course of the study by the Sponsor or its nominated representative. In addition, inspections may be conducted by regulatory authorities at their discretion.

11.9. Monitoring

Data for each subject will be recorded on an eCRF. Data collection must be completed for each subject who signs an ICF.

In accordance with current GCP and ICH guidelines, the study monitor will carry out source document verification at regular intervals to ensure that the data collected in the eCRF are accurate and reliable.

The Investigator must permit the monitor, the IEC/IRB, the Sponsor's internal auditors, and representatives from regulatory authorities' direct access to all study-related documents and pertinent hospital or medical records for confirmation of data contained within the eCRFs.

11.10. Quality Control and Quality Assurance

All aspects of the study will be carefully monitored by the Sponsor or its authorized representative(s) for compliance with applicable government regulations with respect to current GCP and Standard Operating Procedures.

11.11. Data Management and Coding

The Sponsor or the CRO will be responsible for activities associated with the data management of this study. This will include setting up a relevant database and data transfer mechanisms, along with appropriate validation of data and resolution of queries. Data generated within this clinical study will be handled according to the relevant standard operating procedures of the data management and biostatistics departments of Sponsor or the CRO.

Study centers will enter data directly into an EDC system by completing the eCRF via a secure internet connection. Data entered into the eCRF must be verifiable against source documents at the study center. Data to be recorded directly on the eCRF will be identified and the eCRF will be considered the source document. Any changes to the data entered into the EDC system will be recorded in the audit trail and will be FDA CFR 21 Part 11 compliant.

Medical coding will use MedDRA for concomitant diseases and AEs with World Health Organization drug classifications being used for medications.

Missing or inconsistent data will be queried in writing to the Investigator for clarification. Subsequent modifications to the database will be documented.

